#### b. Inclusion/Exclusion

##### **Inclusion Criteria**

- 18 years of age and older
- Reports experiencing current pain not typical of day-to-day experience during Pre-Treatment Pain Questionnaire at the onset of study visit by answering "Yes" to the first question of the questionnaire. There is no specific threshold of how much pain the participant must be in to be eligible for this study. The participant must be experiencing current pain that is not related to day-to-day, normal experiences (such as minor headaches, sprains, and toothaches).
- Scores a 15 on the Glasgow Coma Scale and a 7 or above on the abbreviated Mini Mental Status Exam.
- Patient experiencing pain at University Medical Center Brackenridge or Dell Seton Medical Center in Austin, TX referred to the study by hospital staff.
- Willing and able to provide informed consent and participate in the study visit and study follow-up questionnaire.
- Able to position head completely upright (90 degrees from the ground) in order to view the entirety of the Virtual Reality video.

##### **Exclusion Criteria**

- Hearing or visually impaired where they cannot use the Samsung Gear VR.
- Does not report experiencing current pain during Pre-Treatment Pain Questionnaire at the onset of study visit.
- Scores below a 15 on the Glasgow Coma Scale and/or below a 7 on the abbreviated Mini Mental Status Exam
- Limited mental competency and the inability to give informed, voluntary, written consent to participate.

## Research Proposal

---

- History of motion sickness or cyber sickness and unwilling to watch a 10-minute virtual reality video because of it.
- Unable to position head completely upright (90 degrees from the ground).
- History of seizures.
- Lesions, rashes, or open wounds on face, head, neck, or ears.

c. Benefits

There is no direct benefit to the participant for participating in this study. The possible benefit for the participant from participating in this study is reducing pain they may be experiencing. Societal benefits include diversifying pain management treatments for patients in hospitals to include VR programs. The use of portable and affordable VR technology could be distributed widely and eventually reach patients in all medical and even in home settings. Society could further benefit from using virtual reality for pain management by reducing the use of prescription opioids and subsequently potentially lessening the number of prescription pain reliever drug overdoses in the United States.

d. Risks

The risks associated with participating in this study are minimal. Potential risks include:

- The assessment instruments may cause mild distress because of their focus on emotional topics associated with mental health and pain. If participants are interested in receiving referrals for this distress, they will be instructed to alert research personnel and the personnel will provide the participant with a referral list. Participants can stop the study at any time as a result of this distress with no consequence.
- Cyber sickness, a form of motion sickness, is a potential risk of virtual reality use. Symptoms can include blurred vision, sweating, eyestrain, salivation, headaches, vertigo, dizziness, nausea, and vomiting. Symptoms are temporary and resolve within a few minutes to a few hours. For this reason, we also limit the exposure length to 9-15 minutes. Participants can discontinue the exposure at any time if they experience any of these symptoms. Less than 10% of participants report such symptoms using the old technology. In addition, we expect fewer of these symptoms with this new technology. Participants may stop the study at any time if they begin to experience any of these possible symptoms from experiencing video virtual reality.

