### 4. Procedures

#### **Hospital Study Visit**

Data collection will be completed in a single visit to the participant at University Medical Center Brackenridge Hospital, Dell Seton Medical Center, or **Baylor Scott & White Medical Center Temple** and an online follow-up questionnaire e-mailed to the participant approximately one-week after study visit completion. If email is not available for the follow-up survey, participants will be reached by telephone. Total participation in the hospital visit will be approximately 1 hour. The follow-up survey will take participants 10-15 minutes to complete. Prior to gathering data, research personnel will receive proper training in order to interact with the hospital patients and will follow all hospital procedures during the study visit.

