### Post-Treatment Assessments

Following the 9 minutes of VR exposure or waiting, participants in each condition will complete post-treatment assessments for 5-10 minutes. These assessments will measure pain, presence, mood, negative effects of VR, absorption, human presence, participant's prior familiarity with the locations depicted in the VR video, and their attitude toward the VR session immediately after the treatment. Nausea, dizziness, eyestrain, and head pain is being assessed in an effort to identify the incidence of this component of simulator sickness sometimes associated with VR use (Kennedy et al., 1992). Following the Post-Treatment assessments, the Follow-Up Pain Questionnaire & Present Mood Questionnaire will be administered 10 minutes following the treatment. These follow-up assessments are in place in order to track the lasting pain reduction from the VR treatments.

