### One-week E-mail Follow-up

One-week after participating in the experiment participants will be e-mailed a series of follow-up questionnaires that will include the Follow-Up Pain Questionnaire, Present Mood Questionnaire, and Participant Satisfaction Survey. If participants cannot be reached by email, research personnel will contact them via telephone or a follow-up in person interview.

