The Presence Inventory is adapted from The ITC-Sense of Presence Inventory (Lessiter et al., 2001) and The Igroup Presence Questionnaire (IPQ). It will be used to assess the degree of Spatial Presence (The ITC-Sense of Presence Inventory), Ecological Validity (The ITC-Sense of Presence Inventory & IPQ), and Negative Effects (The ITC-Sense of Presence Inventory).

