### **Collection and Reporting of AEs and SAEs**

Information regarding AEs will be obtained by questioning or examining the participant. At each visit all new complaints and symptoms (i.e., those not existing prior to signing of informed consent) will be recorded on the AE Form. Pre-existing complaints or symptoms that increased in intensity or frequency after having signed the Informed Consent Form will be entered on the AE Form also. All AEs will be characterized in terms of their start and stop dates, start and stop times, intensity, action taken on Intervention, relationship to Intervention, participant outcome and whether or not the AE led to a Serious Adverse Event (SAE). Any clinically relevant increase or decrease to the intensity or frequency of a reported AE will trigger a separate entry on the AE Form. If the event meets the definition of an SAE, the procedure for reporting SAEs will be followed; the event will not be reported on the AE Form also incase the start and stop dates are equal to the start and stop dates of the SAE.

A Serious Adverse Event (SAE) is defined as any untoward medical occurrence that:

- Results in death;
- Is life-threatening;
- Requires in-patient hospitalization or prolongation of existing hospitalization;
- Results in persistent or significant disability/incapacity; or
- Is a congenital anomaly/birth defect.

Medical and scientific judgment will be exercised in deciding whether expedited reporting is appropriate in other situations, such as important medical events that may not be immediately life-threatening or result in death or hospitalization, but may jeopardize the patient or may require intervention to prevent one of the other outcomes listed in the definition above. These will also usually be considered serious too.

All serious events occurring between signing of the Informed Consent Form by the participant and signing of the End of Trial Form by the investigator, except those pre-specified in the protocol, will be reported as soon as practical (within 24 hours of awareness) to the IRB. This includes serious events, which could be associated with the trial procedures, even if occurring outside the treatment period.

Follow-up of SAEs, which occurred during the trial, will in principle take place until resolution of the SAE. Under this protocol, the following event(s) will not be considered as (an) SAE(s) and will not be entered on the SAE form:

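### Cyber sickness is said to last up to a few hours, but its items are scheduled once, within about 10 minutes of the video, and no contact after the visit systematically asks about symptoms or events

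*Protocol*

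**What the plan says.** - **Expected duration.** Section 6.d (Risks) says of cyber sickness: "Symptoms are temporary and resolve within a few minutes to a few hours".
- **Sickness items.** Section 4, Post-Treatment Assessments, gives their purpose: "Nausea, dizziness, eyestrain, and head pain is being assessed in an effort to identify the incidence of this component of simulator sickness". They belong to a battery taking 5-10 minutes straight after the 9-minute exposure. The only instrument described as covering such effects is the Presence Inventory, through its part "Negative Effects (The ITC-Sense of Presence Inventory"). The Section 5 assessment table lists that inventory after treatment only.
- **Rest of the visit.** The same Section 4 text says the "Follow-Up Pain Questionnaire & Present Mood Questionnaire will be administered 10 minutes following the treatment". The visit overview gives 3-5 minutes for these two forms and 3-5 minutes for the open interview.
- **Number of visits.** Under Hospital Study Visit: "Data collection will be completed in a single visit to the participant", followed by a remote questionnaire at about one week.
- **One-week content.** Participants receive "follow-up questionnaires that will include the Follow-Up Pain Questionnaire, Present Mood Questionnaire, and Participant Satisfaction Survey".
- **Adverse events.** Section 6.d, Collection and Reporting of AEs and SAEs, sets the occasion ("At each visit all new complaints and symptoms") and the detail ("All AEs will be characterized in terms of their start and stop dates, start and stop times"). It also asks for serious events to be reported until the End of Trial Form is signed, including those outside the treatment period.
- **Optional waitlist video.** The visit overview lists only the Post-Treatment Pain Questionnaire after it.

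**The concern.** The protocol allows symptoms that outlast the visit, and it wants a stop time for each of them. It collects events at visits, and there is one visit. After that visit no scheduled form carries a symptom or event question.

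What is at stake is the completeness of the safety data. The schedule captures symptoms present just after the video. It is weak on how long they last, and on anything that arises once staff have left. If few lasting or later events are reported, the reader cannot tell whether few occurred or few were asked about. The waitlist patients who choose a video add a group that is exposed with no sickness items scheduled afterwards.

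**Working it through.** The plan states no figure to reproduce. The check adds up the scheduled durations, counted from the end of the video, and then asks what each later contact contains.

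**Inputs** (Section 4 and the visit overview): battery 5-10 minutes; wait 10 minutes; follow-up forms 3-5 minutes; open interview 3-5 minutes.

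**Last sickness item:** no later than the end of the battery, so 10 minutes or less after the video.

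**End of visit.** The 10-minute interval can be read in two ways.
- The wait follows the battery, as the overview orders it: 5 + 10 + 3 + 3 = 21 to 10 + 10 + 5 + 5 = 30 minutes.
- The 10 minutes run from the end of treatment, as the Post-Treatment Assessments text puts it: 10 + 3 + 3 = 16 to 10 + 5 + 5 = 20 minutes.

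Contact therefore ends about 16-30 minutes after the video. As a cross-check, the whole visit is put at about 1 hour. Taking off the 15-minute baseline and the 9-minute video leaves 60 - 15 - 9 = 36 minutes, before any time for consent and headset fitting. The two agree.

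**Set against the stated duration.** The protocol does not say how many hours it means, so I assume 2-4. The gap between the end of the visit and the latest stated resolution is then:
- shortest: 120 - 30 = 90 minutes, or 1.5 hours;
- longest: 240 - 16 = 224 minutes, or about 3.7 hours.

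A symptom that clears within minutes falls inside the visit. The gap concerns the upper part of the protocol's own range.

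**What each later contact asks**

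| Contact | Scheduled content | Symptom or event question |
|---|---|---|
| In-visit follow-up | Pain and mood | None listed |
| Open interview | Comfort, usefulness, general experience | Unstructured |
| Optional waitlist video | Post-Treatment Pain Questionnaire | None listed |
| One week | Pain, mood, satisfaction | None listed; some free text |
| Medical record | Includes progress notes | Only with signed HIPAA authorization |

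The follow-up pain form asks about the preceding 10 minutes (Section 5). At one week it therefore says nothing about head pain in the hours after the visit. The satisfaction survey includes a global rating of change, which is not a symptom question either.

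**Adverse event rule against the schedule.** The rule ties collection to visits. With one visit ending at 16-30 minutes, a non-serious symptom still present at that point has no scheduled occasion on which its stop time would be obtained.

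**The case against.** A fair defence has five parts.

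1. **Events are asked about.** The adverse event section says information comes from questioning or examining the participant, and this covers the whole visit. The open interview comes after the sickness items and asks about comfort. The one-week survey has open-ended questions, and progress notes are available for patients who authorize access. This stands. A reader might infer that later symptoms cannot be recorded at all, or that nobody asks; the documents do not support that. These routes are, however, confined to the visit, unprompted or available for only some patients.

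2. **The risk statement is about duration.** It does not speak of delayed onset, and a symptom that begins during the video and lasts for hours is still present when the items are asked. The items' stated purpose is incidence, for which one administration after exposure is reasonable. This stands. Incidence at the end of exposure is captured in the two VR arms; duration and stop time are not.

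3. **The trial has no aim of proving that symptoms are temporary.** This stands. The sentence is background to the risk section, and the point rests on the adverse event section's own requirement for stop times.

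4. **The serious event rule is not contradicted.** Its 24-hour clock runs from awareness, so it works as written. This stands. What remains is that no scheduled contact after the visit is designed to create that awareness.

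5. **The AE Form's absence from the visit overview and assessment table is layout.** Adverse events have their own section, as does medical record collection, which is also absent from both lists. I accept this and give the absence no weight.

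**Conclusion.** The point holds as a gap in systematic ascertainment. The sickness items are scheduled once, 10 minutes or less after the video. Contact ends at about 16-30 minutes, while the protocol allows symptoms of up to a few hours and requires stop times for every event. No scheduled contact after the visit systematically asks about symptoms or events. Waitlist patients who take the optional video have no sickness items after it, although adverse event questioning at the visit and the open interview still apply to them.

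Under the assumed 2-4 hours, the visit ends 1.5 to 3.7 hours before the latest stated resolution. This is clock time, not a share of events missed; the documents give no basis for estimating that share. The conclusion holds under either reading of the 10-minute interval. It rests on one inference: that the four items sit in the Presence Inventory, or at least in the post-treatment battery, and are not repeated.

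This does not threaten the efficacy comparison. It should be corrected because it limits what the safety data can say and because the correction is cheap.

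**What to change.** 1. Repeat the four sickness items at the existing in-visit follow-up contact, and give them to waitlist patients after any optional video.
2. Add one question to the existing one-week form, in all arms, on new or worse symptoms or hospital events since the visit, with start, duration and whether care was needed. Have replies checked on receipt so that a serious event comes to the team's attention.
3. Enter every endorsed sickness item on the AE Form.

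If the one-week question is not wanted, reconcile Hospital Study Visit, Post-Treatment Assessments, One-week E-mail Follow-up, the visit overview, the assessment table and the adverse event section. That means limiting the event window and the stop-time requirement to what the visit can observe.

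The cost is a few items at contacts already scheduled and a small amendment. One-week recall of the start and end of a symptom lasting minutes or hours is imperfect, and non-responders at one week stay unknown. Waitlist answers must be read with whether the patient took the optional video.

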### **Protection of Human Participants from Research Risk**

*Adequacy of Protection Against Risks:* The PI, [name]., is available for intervention as needed and back-up plans are established including referral to a hospital emergency department. These safety procedures have been effective in dealing with adverse physical and mental health events in previous and ongoing studies. Upon study completion, all participants will be referred to follow-up care if needed.

## Research Proposal

---

Persons who express suicidal ideation (or other forms of serious threat to themselves or others, or who are gravely disabled due to a mental disorder) at any time they are in contact with the study personnel will receive the usual ethically and legally appropriate courses of action. This would include assessment of the seriousness of danger or disablement, referral for immediate crisis management (e.g., hotlines, crisis centers, hospitals), or contacting emergency psychiatric teams or police if necessary. Study personnel who have direct contact with study participants (e.g., telephone interviewers, laboratory assessors, scheduling staff) will be trained in methods of crisis management.

To deal with the potential risk of loss of privacy (judged to be minimal), we will maintain confidentiality by numerically coding all data, by disguising identifying information, and by keeping all data in locked file drawers. Participant information will be accessible only to research staff. Identifying information will not be reported.

### **Collection and Reporting of AEs and SAEs**

Information regarding AEs will be obtained by questioning or examining the participant. At each visit all new complaints and symptoms (i.e., those not existing prior to signing of informed consent) will be recorded on the AE Form. Pre-existing complaints or symptoms that increased in intensity or frequency after having signed the Informed Consent Form will be entered on the AE Form also. All AEs will be characterized in terms of their start and stop dates, start and stop times, intensity, action taken on Intervention, relationship to Intervention, participant outcome and whether or not the AE led to a Serious Adverse Event (SAE). Any clinically relevant increase or decrease to the intensity or frequency of a reported AE will trigger a separate entry on the AE Form. If the event meets the definition of an SAE, the procedure for reporting SAEs will be followed; the event will not be reported on the AE Form also incase the start and stop dates are equal to the start and stop dates of the SAE.

A Serious Adverse Event (SAE) is defined as any untoward medical occurrence that:

- Results in death;
- Is life-threatening;
- Requires in-patient hospitalization or prolongation of existing hospitalization;
- Results in persistent or significant disability/incapacity; or
- Is a congenital anomaly/birth defect.

Medical and scientific judgment will be exercised in deciding whether expedited reporting is appropriate in other situations, such as important medical events that may not be immediately life-threatening or result in death or hospitalization, but may jeopardize the patient or may require intervention to prevent one of the other outcomes listed in the definition above. These will also usually be considered serious too.

All serious events occurring between signing of the Informed Consent Form by the participant and signing of the End of Trial Form by the investigator, except those pre-specified in the protocol, will be reported as soon as practical (within 24 hours of awareness) to the IRB. This includes serious events, which could be associated with the trial procedures, even if occurring outside the treatment period.

Follow-up of SAEs, which occurred during the trial, will in principle take place until resolution of the SAE. Under this protocol, the following event(s) will not be considered as (an) SAE(s) and will not be entered on the SAE form:

- Pre-planned hospitalizations for diagnostic, therapeutic, or surgical procedures for a pre-existing condition that did not worsen during the course of a clinical trial. These pre-planned hospitalizations will be entered on the medical history form, including the condition requiring hospitalization.
- Hospitalizations for uncomplicated delivery.

All SAEs (i.e. including serious events occurring outside the treatment period) will be reported as soon as practical (within 24 hours of awareness) to the IRB. Reporting of an SAE will be done by means of the SAE form. For each SAE, the investigator fills out this SAE form (as complete as possible) and sends the form and all available supporting documentation by fax or scan.

e. Recruitment

Our Seton PI, [name], will connect research personnel with hospital staff at UMCB and DSMC who care for patients experiencing pain. Hospital staff will refer patients to research personnel that meet eligibility criteria for the study and may be a potentially eligible participant. Patient information necessary to conduct an in-person recruitment visit by study personnel (patient name and hospital room number) will be shared by hospital staff with research personnel through the standard secure email (Ascension Secure E-mail Portal) or texting (TigerText) applications used by UMCB and DSMC. Both of these applications are regularly used by UMCB and DSMC staff to share Protected Health Information (PHI) with hospital staff. Ascension Secure E-mail Portal and TigerText keep messages confidential and are HIPAA compliant. Additionally, potential participant information may be shared with research personnel in-person. Hospital staff may supply potential participants with information regarding the study found in the Recruitment Announcement, but will not be involved with direct recruitment. All direct recruitment will be conducted by research personnel. This method of recruitment is the standard used by UMCB and DSMC and is the preferred manner of recruitment by hospital staff.

Our BSWMCT PI, [name], will connect research personnel with hospital staff at BSWMCT who care for patients experiencing pain. Hospital staff will refer patients to research personnel that meet eligibility criteria for the study and may be a potentially eligible participant. Patient information necessary to conduct an in-person recruitment visit by study personnel (patient name and hospital room number) will be shared by hospital staff with research personnel in-person, over the phone, or in email over the secure hospital network. All direct recruitment will be conducted by research personnel

Research personnel will meet with the potential participant in their hospital room to recruit the patient for the study. If the patient is interested in participating, the research

